7.5. Exclusion criteria

- Inclusion criteria failure
- Concomitant anticancer treatment
- Known hypersensitivity to any component of study drugs or ingredients
- Pregnancy or breast feeding
- Patients with rare hereditary problems of galactose intolerance, the Lapp lactase deficiency or glucose-galactose malabsorption
- Neuromuscular disorders (e.g. Charcot-Marie Tooth disease)
- Uncontrolled intercurrent illness or active infection
- Unable for medical follow-up (geographic, social or mental reasons)

7.6. Life style guidelines

Patients with reproductive potential must agree to use effective contraception during the period of therapy. *Men should be advised not to father a child up to 6 months after receiving the last dose. Women of childbearing potential should be advised to use effective contraception to avoid pregnancy up to 6 months after the last dose of study treatment.*

7.7. Patient enrolment

According to the Good Clinical Practice (GCP) guidelines, all inclusion/exclusion criteria will be checked during the registration procedure. A registration number that further identifies the patient within the centre will be allocated to the patient.

The following procedures should be performed before completing the registration form:

- Informed consent leaflet should be signed by patient or the parents or legal representative of patient and the investigator before starting any study procedure ;
- All selection procedures should be performed as per protocol ;
- After patient registration, the patient identification number and treatment arm allocated will be retained within the study even if the patient is withdrawn from the study before the first study drug administration. New patients must always be allocated a new number.

The procedure for enrolling patients will be detailed for each participating centre. The TenAlea software program via internet will be the preferred system. It is possible to use a backup procedure by faxing the registration form to the following address:

Clinical Research Integrated Unit / Sponsor Unit

Centre Oscar Lambret – Lille - France

[contact] - [contact]

7.8. Withdrawal from study treatment

Patients will be considered withdrawn from study for one of the following reasons:

- Progressive disease
- Global deterioration of health status
- Unacceptable toxicity (Noted on CRF adverse event page)
- Cycle of treatment delayed by more than 2 weeks
- Investigator decision
- At the request of the patient or a representative
- Lost to follow up
- Death of patient

This section only concerns treatment withdrawal, since the main statistical analysis will be performed on the intent to treat patient population. Follow-up visits are planned after “withdrawal from study treatment”.

8. STUDY TREATMENT

Enrolment will take place after the patient or patient's parent or legal guardian have given written informed consent and eligibility has been established.

A patient identification number will be assigned, and this number will be retained for the patient throughout the duration of study participation. After the patient is enrolled, study treatment will be initiated as outlined in section 7.7.

8.1. Dispensing, storage of the investigational drug

In this clinical trial, vincristine, irinotecan and TMZ are all considered as Investigational Medicinal Products (IMPs). For the purposes of the protocol, the term "study medication" or "investigational agent" refers to the combination of vincristine, and irinotecan with or without TMZ.

The IMPs will be used from Normal Hospital Stock. In The Netherlands, neither TMZ, nor cefixim used as prophylactic treatment, are registered. This drugs will be considered as investigational medicinal products and will be provided as study medication (see Appendix 11 for TMZ and cefixime management in The Netherlands).

8.2. Drug supplies

The investigator/pharmacist must maintain an accurate record of the dispensing of the study drug in a standard drug accountability ledger, a copy of which must be sent to Sponsor at the end of the study.

An accurate record of the date and amount of study drug dispensed to each patient must be available for inspection at any time.

8.2.1. Vincristine

Vincristine is available commercially in 1mg/ml vials (1 mg, 2 mg, 5 mg vials with 10 ml diluent).

Reconstituted injection is stable for 14 days (2-8°C), refer to local guidelines.

Administration will be made by bolus injection taking care to avoid extravasion and must comply with guidance on administration of vinca alkaloids as per NPSA/2008/RRR004.

8.2.2. Irinotecan

The intravenous formulation of irinotecan (Irinotecan hydrochloride trihydrate) is available commercially in 20 mg/ml vials.

For intravenous administration, irinotecan should be diluted with 5% dextrose in water or 0.9% sodium chloride solution to a final concentration of 0.12-2.8 mg/ml and infused IV over 60 minutes. Nothing else should be added to the bag. The total administered dose of chemotherapy may be rounded up or down within a range not exceeding 5% of the actual calculated dose. After reconstitution, irinotecan is stable for 24 hours at room temperature and in ambient fluorescent lighting.

Drug handling precautions for cytotoxic drugs should be followed. Avoid contact or inhalation.

8.2.3. Temozolomide

TMZ, an imidazotetrazine derivative, is available commercially as capsules for oral administration. TMZ contains lactose. Each capsule will contain 5, 20, 100, 140, 180 or 250 mg of the active ingredient TMZ. TMZ must be stored protected from light. Do not store above 30°C.

If a capsule becomes damaged, avoid contact of powder contents with skin or mucous membrane. If contact does occur, wash the affected area. Capsules should not be chewed. Keep capsules out of reach and sight of children, preferably in a locked cupboard.

8.3. Summary of Products Characteristics

Investigators must refer to the informations contained in the country-specific applicable Summary of Products Characteristics (SPCs) of Marketing Authorized products for the management of patients, particularly with regard to contraindications, warnings and precautions for use, dose adjustments in case toxicity, monitoring of patients and prohibited drugs or drugs to use with caution. Coordinating centres make available the official and updated versions of the SPCs for study drugs used in their respective territory.

9. TREATMENT ADMINISTRATION

9.1. Starting doses and schedules

ARM A		
D1 and D8 Vincristine	1.5 mg/m ² /d – IV bolus (0.05 mg/kg for patient ≤ 10 kg)	3 weekly
D1 to D5 Irinotecan	50 mg/m ² /d – IV over 1 hour	3 weekly
ARM B		
D1 to D5 Temozolomide	125 mg/m ² /d - PO	3 weekly
D1 and D8 Vincristine	1.5 mg/m ² /d – IV bolus (0.05 mg/kg for patient ≤ 10 kg)	3 weekly
D1 to D5 Irinotecan	50 mg/m ² /d – IV over 1 hour	3 weekly

Vincristine: The dose of vincristine will be 1.5 mg/m² or 0.05 mg/kg for patient ≤ 10 kg (maximum 2.0 mg) and will be administered by direct intravenous infusion on day 1 and day 8 of each course, before irinotecan. Administration must comply with guidance on administration of vinca alkaloids as per NPSA/2008/RRR004.

Irinotecan: The dose of irinotecan will be 50 mg/m²/day. Irinotecan will be given intravenously infusion over 1 hour on days 1-5, one hour following the administration of TMZ. In absence of contraindications (known allergies), **systematic treatment with oral cefixime 8 mg/kg once a day (maximum daily dose 400 mg) is recommended and will be started 2 days before chemotherapy until day 7** (see Appendix 11 for cefixime management in The Netherlands).

Temozolomide: will be given according to the randomization: The starting dose of TMZ will be 125 mg/m²/day. The dose of TMZ will be escalated to 150 mg/m²/day at cycle 2 for patients who do not experience ≥ grade 3 toxicity of any kind. The dose of TMZ should be rounded to the nearest 5 mg. TMZ will be given orally, on an empty stomach, prior to vincristine and irinotecan, on days 1-5 repeated every 3-weeks. If the patient vomits within 20 minutes after TMZ, the dose will be re-administered. The capsules must be swallowed whole with a glass of water. For young children and patients who have difficulty swallowing capsules, the full daily dose of TMZ capsules should be placed

in 10-30 ml fruit juice or compote and administered after the capsules have been allowed to soften for 15-20 minutes or according to normal local practice for patients in the United Kingdom (see Appendix 12).

Treatment will continue until disease progression, unacceptable toxicity or the patient's desire to discontinue therapy. Local treatment is allowed after 2 cycles.

Patients must have evidence of recovery from all prior cycle toxicity and the ANC must be > 1000/mm³ and platelets > 100 000/mm³ before receiving the next cycle of therapy. If initiation of the next treatment cycle is delayed by more than 2 weeks, the patients should be discontinued from the study.

In the absence of clinically progressive disease, patients should receive at least 2 cycles of VIT or VI prior to the first evaluation on study treatment.

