2.1 of 4 May 2012 including second amendment (d)	201116/SA2 201116/SA3 (re-submission)	25 May 12	6 Jun 12	10 Apr 12		8 Mar 13		7 Sept 2012 (Barcelona)			23 Jul 2012	10 Jul 2012.
3.0 of 30 Jan 2014 including third amendment (e)	201116/SA4	18 Mar 14	4 Apr 14	8 Apr 14			10 April 2014	4 April 2014				
4.0 of 1st Dec 2015 including 4th amendment (f)	201116/SA5	27 Jan 2016	1st Mar 2016	5 Jul 2016								
4.1 of 13 July 2016 including non substantial amendment (g)	Not applicable	Not applicable	Not applicable									
5.0 of 9th July 2018 including 5th amendment (h)	Not applicable	Not applicable	20 Aug 2018	2 Oct 2018								
5.1 of June 24th 2019 including non-substantial amendment (i)	Not applicable	Not applicable	Not applicable	Not applicable								

NCA: National Competent Authority, EC: Ethic Committee

- (a) Removal of pharmacogenetic study, trial site list update, clarifications requested by the NCRN, correction of typing errors, addition of formulae for calculation of creatinine clearance (Appendix 8)
- (b) Funding arrangement for cefixime and temodal, drug management in The Netherlands (Appendix 11)
- (C) Addition of Guidelines for administering temozolomide to patients in the United Kingdom who have difficulty swallowing temozolomide capsules (Appendix 12)
- (d) Additional instructions about vincristine dose adjustments, and in case of bone marrow disease; clarification of SAE reporting; update of the study calendar; correction of typing errors
- (e) information about hepatic toxicities occurring in patients treated with Temozolomide, revision of Temodal SmPC, revision of Helsinki declaration, update of staff contacts
- (f) Addition of 40 extra patients with recurrent RMS, and non substantial modifications (changes in staff list, protocol clarifications)
- (g) update of staff contact list (sponsor)
- (h) addition of contraindications following update of irinotecan's SmPC, and non substantial modifications (changes in staff list, clarifications of biostatistical considerations, update of temozolomide and vincristine's SmPC without impact on patient's safety)
- (g) removal of a withdrawal criterion; definition of the Last Visit of the Last Subject (LVLS) as the last VI/VIT administration + 6 months to have relevant data in terms of response after 2 cycles.

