7.4. Inclusion criteria

Patients must satisfy all the following entry criteria before they are allowed to participate in the study.

TUMOR CHARACTERISTICS:

- Histologically or cytologically confirmed diagnosis of rhabdomyosarcoma (new biopsy recommended)
- Any Relapsed / progressive disease (in patients who have already presented a response to chemotherapy)

OR

- Refractory disease (defined as progression after receiving chemotherapy without prior response)
- Patients must have measurable disease defined as lesions that can be measured in 3 dimensions by medical imaging techniques such as CT or MRI. Ascites, pleural fluid, bone marrow disease alone and lesions seen on Tc scintigraphy or PET scan only are not considered measurable.

PATIENT CHARACTERISTICS:

- Age > 6 months and ≤ 50 years
- Karnofsky performance status (PS) 70-100% (for patients > 12 years of age)
OR Lansky Play Score 70-100 % (for patients ≤ 12 years of age)
- Life expectancy ≥ 12 weeks
- Adequate bone marrow function :
 - Absolute neutrophil count ≥ 1000/mm³
 - Platelet count ≥ 100,000/mm³ (transfusion independent)
 - Hemoglobin ≥ 8.5 g/dL (transfusion allowed)

- In case of bone marrow disease:
 - Absolute neutrophil count $\geq 500/\text{mm}^3$
 - Platelet count $\geq 75,000/\text{mm}^3$
- Adequate renal function
 - Serum creatinine $\leq 1.5 \times \text{ULN}$ for age
 - If serum creatinine $> 1.5 \text{ ULN}$, creatinine clearance (or radioisotope GFR) must be $\geq 70 \text{ ml/min/1.73 m}^2$
- Adequate hepatic function :
 - Total bilirubin ≤ 1.5 times upper limit of normal (ULN) for age, except if the patient is known to have Gilbert's syndrome
 - ALT and AST $\leq 2.5 \times \text{ULN}$ for age
- Negative pregnancy test in females with childbearing potential
- Fertile patients must use effective contraception
- No active $>$ grade 2 diarrhea or uncontrolled infection
- No other malignancy, including secondary malignancy
- Patient affiliated with a health insurance system. Applicable for French patients only
- Written informed consent of patient and/or parents/ guardians

PRIOR OR CONCURRENT THERAPY:

- More than 3 weeks since prior radiation therapy to the site of any progressive lesion that will be identified as a target lesion to measure tumor response
- At least 3 weeks since prior myelosuppressive therapy (6 weeks for nitrosourea, 2 weeks for vincristine, vinorelbine, vinblastine and low-dose cyclophosphamide)

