9.2. Dosage adjustments

Patients should be carefully monitored for toxicity. After the initial treatment cycle, dose reductions and/or administration delays will be decided using specific predefined rules to accommodate individual tolerance of treatment and maintain optimal dose intensity. All toxicities will be graded according to version 4.0 of the NCI CTCAE. Doses are to be adjusted based on the most severe toxicity that the patient experiences related or possibly related to the study treatment between each cycle of treatment. For hematological toxicities, the guiding principle is that the full doses of both drugs will be administered only if toxicities have recovered to ANC ≥ 1000/mm³ or and platelet count ≥ 100 000/L, or ANC ≥ 500/mm³ or and platelet count ≥ 75 000/mm³ in case of bone marrow disease, by day 21 after the start of the cycle

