11.1.3. Objective tumour response and progression

Primary efficacy endpoint

The primary efficacy endpoint is defined as the proportion of patients who had a documented complete or partial tumour response occurring after the first 2 cycles of treatment which must be confirmed by a follow-up objective tumour assessment obtained within 4-5 weeks after the initial documentation.

Secondary endpoints

Secondary efficacy endpoints are defined as follows:

- The best overall response is the best response recorded from the start of the treatment until disease progression/recurrence (taking as reference for PD the smallest measurements recorded since the treatment started) over the whole treatment duration. It must be confirmed by a follow-up objective tumour assessment obtained within 4-5 weeks after the initial documentation.
- Duration of tumour response: the time from first documentation of objective tumour response to the first objective or clinical documentation of progression
- Time to treatment failure: the time from the date of first treatment administration to the first documentation of tumour progression, discontinuation of study treatment before one year, or death, whichever occurs first
- Progression-free survival (PFS): the time from the date of first treatment administration to the date of first objective or clinical documentation of tumour progression or death due to any cause
- Overall survival (OS): the time from the date of first treatment administration to date of death

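### Section 9.1 requires counts above 1000/100 000 for every next cycle, with no exception for bone marrow disease, although 7.4 admits such patients at 500/75 000 and 9.2 accepts those counts as recovery

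*Protocol*

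**What the plan says.** Protocol 7.4 sets a general entry level of ANC ≥ 1000/mm³ and platelets ≥ 100 000/mm³. Under the line "In case of bone marrow disease" it gives lower levels of 500/mm³ and 75 000/mm³.

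Section 9.1 governs retreatment: "the ANC must be > 1000/mm³ and platelets > 100 000/mm³ before receiving the next cycle of therapy". It adds: "If initiation of the next treatment cycle is delayed by more than 2 weeks, the patients should be discontinued from the study". Section 7.8 lists the same event among its reasons for withdrawal from study treatment: "Cycle of treatment delayed by more than 2 weeks". Neither section mentions bone marrow disease.

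Section 9.2 says that after the first cycle "dose reductions and/or administration delays will be decided using specific predefined rules". It makes full dose conditional on recovery by day 21 to the general counts, or to "ANC ≥ 500/mm³ or and platelet count ≥ 75 000/mm³ in case of bone marrow disease". The adjustment tables in 9.2.1, one per arm, print only 1000 and 100 000 in their haematological rows.

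Section 11.1.3 counts "discontinuation of study treatment before one year" as an event for time to treatment failure. Section 12.2 defines a patient as evaluable for response only after at least 2 cycles and an available tumour evaluation at 2 cycles. The main analysis there is by intention to treat.

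**The concern.** A patient with marrow involvement may have low counts because of the disease and not because of the drugs. Sections 7.4 and 9.2 both allow for this; the rule that decides whether the next cycle may start does not. Followed literally, 9.1 withholds treatment from a patient whose counts are no worse than those that made the patient eligible, and after two weeks it ends treatment.

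At stake are avoidable under-treatment and discontinuation in a small subgroup, and different handling of the same patient by sites that follow 9.1 and sites that follow 9.2. On the statistical side, an event would enter time to treatment failure that reflects neither progression nor new toxicity, and a patient could leave the per-protocol response set.

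**Working it through.** No figure of the plan is in question, so the check compares the stated thresholds (ANC / platelets, per mm³). In 9.2, the doubled conjunction between the two counts is read as *and*, in line with 7.4, and the general platelet count, printed per litre, is read as per mm³.

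| Section | What it decides | General | Bone marrow disease |
|---|---|---|---|
| 7.4 | entry | ≥ 1000 / ≥ 100 000 | ≥ 500 / ≥ 75 000 |
| 9.1 | start of next cycle | > 1000 / > 100 000 | none given |
| 9.2 | full dose, by day 21 | ≥ 1000 / ≥ 100 000 | ≥ 500 / ≥ 75 000 |
| 9.2.1 tables | reduction or stop | 1000 / 100 000 | none given |

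**Range of conflict.** It covers bone marrow disease with ANC ≥ 500 and platelets ≥ 75 000, but ANC ≤ 1000 or platelets ≤ 100 000. The range is 1000 − 500 = 500/mm³ wide for ANC and 100 000 − 75 000 = 25 000/mm³ wide for platelets.

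**Patient 1 (illustrative).** Bone marrow disease, ANC 600 and platelets 80 000 at entry, on day 21 of cycle 1 and afterwards.
- 7.4: eligible, since 600 ≥ 500 and 80 000 ≥ 75 000.
- 9.2: recovered for full dose.
- 9.1: no cycle 2, since 600 and 80 000 are both below the required counts.
- Last permitted start under 9.1 and 7.8: 21 + 14 = day 35. In arm B the table also orders a stop if counts are still below 1000/100 000 on day 34.
- Result: treatment ends after 1 cycle, where 10.2.3 foresees up to 12. This is a time-to-treatment-failure event at about five weeks. With fewer than 2 cycles the patient is also non-evaluable for response under 12.2.

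**Patient 2 (illustrative).** Bone marrow disease, ANC 700 on day 21 and above 1000 on day 26, platelets above 100 000 throughout. Read in sequence, 9.1 delays the cycle by 26 − 21 = 5 days and 9.2 then allows full dose, because 700 ≥ 500 by day 21. The tables can be read in two ways:
- If recovery has the meaning given in 9.2, the day-21 row applies and no dose changes.
- If recovery means the 1000/100 000 printed in the row, the row for days 22 to 28 applies. Irinotecan falls from 50 to 40 mg/m² in arm A; temozolomide falls one level in arm B (125 to 100, or 150 to 120 mg/m²).

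So under the sequential reading the 9.2 exception can never permit an on-time cycle. What it can do, spare a dose reduction in a late one, depends on how the tables are read.

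**Dose intensity from delay alone.** Over one interval it is 21/(21 + delay): 21/28 = 75% for 7 days and 21/35 = 60% for 14 days. These values hold for any delay of that length, whatever the cause, and do not measure this defect specifically.

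**The case against.** The strongest reply is that the sections do not collide: 9.1 says when a cycle may start and 9.2 says at what dose. The condition in 9.2 is one for full dose and gives no right to restart, and Patient 2 shows that the exception then has a use. This stands, so it would be too strong to call the sections irreconcilable or the exception void. It does not remove the problem: 9.2 also claims to decide delays, its lower counts are tied to the planned restart day, and Patient 1 is still stopped.

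A second reply is that a site could take 9.2 as the specific rule for marrow disease and let it override 9.1. That is possible, but nothing in the text says so, and 9.1 is worded for all patients.

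Third, the subgroup is narrow. It needs marrow disease, a measurable lesion as well (7.4 does not accept marrow disease alone as measurable), and counts within the range at restart. Discontinuation further needs them to stay there for more than two weeks. This stands.

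A reader might also infer from the amendment list, where the second amendment is described as "Additional instructions about vincristine dose adjustments, and in case of bone marrow disease", that 9.1 was overlooked then. The list does not say which sections changed, so it does not support that. The inconsistency lies wholly in the current text.

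**Conclusion.** The inconsistency is real and should be fixed, but its reach is limited. Read literally, 9.1 delays and then discontinues a marrow-disease patient who has returned to counts that the protocol accepts for entry and for full dose. The consequences are a time-to-treatment-failure event and, if it happens before cycle 2, loss from the per-protocol response analysis.

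The protocol does not give the number of such patients; it is probably small. The patient remains in the intention-to-treat main analysis, and 7.8 foresees follow-up after treatment withdrawal. Sample size, error rates and the decision rule do not change.

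Two stronger conclusions might be drawn and are not supported. One is that patients have been wrongly stopped: the documents hold no such data, and sites may have followed 9.2. The other is a risk of overdosing: 9.1 is the stricter rule, so the risk is under-treatment. The verdict assumes that 9.1 is applied as worded and that 9.2 requires both counts.

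**What to change.** In 9.1, state that the next cycle may start at ANC ≥ 1000/mm³ and platelets ≥ 100 000/mm³ or, in case of bone marrow disease, at ANC ≥ 500/mm³ and platelets ≥ 75 000/mm³. This also removes the difference between > in 9.1 and ≥ in 9.2. Above the two tables in 9.2.1, add a line saying that recovery is judged by the thresholds in 9.2, including those for bone marrow disease.

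The drafting is two sentences, but the change is more than editorial. It relaxes a retreatment condition in a small subgroup of both arms, so it needs clinical sign-off and probably a substantial amendment under 13.4, followed by information to sites. No statistical parameter has to be recalculated.

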9.2.1. Vincristine, Irinotecan and Temozolomide

Dose levels for dose adjustment

Starting dose	Reduction (20%) dose level -1	Reduction (20%) dose level -2
Temozolomide		
125 mg/m ² /dx5 q 3 wks	100 mg/m ² /dx5 q 3 wks	75 mg/m ² /dx5 q 3 wks
150 mg/m ² /dx5 q 3 wks	120 mg/m ² /dx5 q 3 wks	90 mg/m ² /dx5 q 3 wks
Irinotecan		
50 mg/m ² /dx5 q 3 wks	40 mg/m ² /dx5 q 3 wks	30 mg/m ² /dx5 q 3 wks
Reduction (50%) dose level -1		
Vincristine		
1.5 mg/m ² /d (maximum 2mg) direct IV infusion at d1 and d8 q 3 wks (0.05 mg/kg for patient ≤ 10 kg)	0.75 mg/m ² (maximum 1mg) direct IV infusion at d1 and d8 q 3 wks (0.025 mg/kg for patient ≤ 10 kg)	

Study treatment dose reduction or discontinuation

Arm A (VI)

Type of toxicity	Dose modification at first occurrence	Dose modification at second occurrence

 ANC < 1000/mm³ or Platelet count < 100000/mm³ But recovered on day 21 after the start of a cycle 	
 No dose modification 	
 No dose modification

 ANC < 1000/mm³ or Platelet count < 100000/mm³ But recovered between 22 to 28 after the start of a cycle 	
 Decrease irinotecan to dose level -1 	
 Decrease irinotecan to dose level -2

 ANC < 1000/mm³ or Platelet count < 100000/mm³ But recovered between 29 to 34 after the start of a cycle 	
 Decrease irinotecan to dose level-2 	
 Discontinue study treatment

 Grade 3 and 4 diarrhea despite maximum loperamide therapy 	
 Decrease Irinotecan dose to dose level -1 If the same level of toxicity persists > 2 weeks despite suitable symptomatic treatment, discontinue study treatment If diarrhea is ongoing on day 21, delay next cycle for up to 2 weeks until diarrhea resolves to ≤ grade 1 If the diarrhea does not resolve after a 2-week delay, the patient should discontinue study treatment 	
 Decrease Irinotecan dose level -2 If the same level of toxicity persists > 2 weeks despite suitable symptomatic treatment, discontinue study treatment If diarrhea is ongoing on day 21, delay next cycle for up to 2 weeks until diarrhea resolves to ≤ grade 1 If the diarrhea does not resolve after a 2-week delay, the patient should discontinue study treatment

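### Patients with bone marrow disease can meet the section 9.2 count threshold for full doses, yet be barred from the next cycle, and eventually discontinued, by section 9.1.

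*Protocol*

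**What the plan says.** Four places in the Protocol set blood-count limits that bear on whether and how a patient is treated.

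- **Section 7.4 (Inclusion criteria)** has a separate entry, headed "In case of bone marrow disease", that admits these patients at ANC ≥ 500/mm³ and platelets ≥ 75,000/mm³. Other patients need 1000 and 100,000/mm³.
- **Section 9.1 (Starting doses and schedules)** sets the condition for starting any later cycle: "the ANC must be > 1000/mm³ and platelets > 100 000/mm³ before receiving the next cycle of therapy". The next sentence adds: "If initiation of the next treatment cycle is delayed by more than 2 weeks, the patients should be discontinued from the study". Section 7.8 also lists a delay of more than 2 weeks as a reason for withdrawal. Neither section mentions bone marrow disease.
- **Section 9.2 (Dosage adjustments)** gives the guiding principle for haematological toxicity: "full doses of both drugs will be administered only if toxicities have recovered to ANC ≥ 1000/mm³ or and platelet count", followed by a lower alternative of ANC ≥ 500/mm³ and "platelet count ≥ 75 000/mm³ in case of bone marrow disease, by day 21 after the start of the cycle". The general platelet limit in that sentence is printed as "platelet count ≥ 100 000/L".
- **Section 9.2.1 (dose tables)** describes the haematological rows of both arms as "ANC < 1000/mm³ or Platelet count < 100000/mm³". Three rows then divide patients by when the counts recovered: day 21, days 22 to 28, or days 29 to 34. The Arm A consequence at first occurrence for days 22 to 28 is "Decrease irinotecan to dose level -1". The Arm B table has a further row that discontinues treatment if counts are still below the limits on day 34. Neither table has a row or footnote for bone marrow disease.

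**The concern.** The lower limits for bone marrow disease appear at entry and in the full-dose recovery principle, but not in the rule that decides whether the next cycle may start. No text says which limit governs. A site that applies 9.1 literally withholds a cycle from a patient who has recovered to the marrow-disease threshold. If the counts stay there, that site discontinues the patient at values that qualified the patient for the trial. A site that takes the 9.2 marrow clause as its working limit would treat.

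The stake is consistent and safe dosing in a small subgroup. There are also knock-on effects on how such patients are classified. Section 12.2 counts as evaluable for the main objective only patients who received at least 2 cycles and have a tumour evaluation at that point. A patient stopped after cycle 1 leaves that set while remaining in the intent-to-treat population. Section 11.1.3 counts discontinuation before one year as an event for time to treatment failure. A stop caused by this gap in the rules would be recorded there like any other.

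**Working it through.** The protocol states no figure to reproduce. The check is a comparison of thresholds, followed by one worked case.

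**Limits that apply to a patient with bone marrow disease**

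| Place | Decision | ANC (/mm³) | Platelets (/mm³) | Marrow exception? |
|---|---|---|---|---|
| 7.4 | Entry | ≥ 500 | ≥ 75,000 | Yes |
| 9.2 | Full doses, recovery by day 21 | ≥ 500 | ≥ 75,000 | Yes |
| 9.1 | Start of next cycle | > 1000 | > 100,000 | No |
| 9.2.1, Arm B day-34 row | Discontinue if below | 1000 | 100,000 | No |
| 9.2.1, 'recovered' rows, both arms | Dose level | 1000 | 100,000 | Not stated; depends on the meaning of 'recovered' |

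**Zone of disagreement between 9.1 and 9.2.** The 9.2 limit is met and the 9.1 condition is not when ANC ≥ 500 and platelets ≥ 75,000/mm³, but ANC ≤ 1000 or platelets ≤ 100,000/mm³.

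**Worked case.** Take a marrow-disease patient with ANC 700/mm³ and platelets 80,000/mm³ on day 21.

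1. Section 7.4: 700 ≥ 500 and 80,000 ≥ 75,000, so these counts would have met the entry rule.
2. Section 9.2: the same two comparisons hold, so the recovery threshold for full doses is met.
3. Section 9.1: 700 is not above 1000 and 80,000 is not above 100,000, so the next cycle may not start.
4. If the counts stay there, 9.1 and 7.8 require discontinuation in either arm once the delay exceeds 2 weeks. In Arm B the day-34 row requires the same. Arm A has no such row, so there the stop comes from the delay rule alone.

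**Dose reduction, conditional on how the tables are read.** Suppose the counts pass 1000 and 100,000/mm³ only after day 21.

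- *If 'recovered' is read through 9.2*, the patient counts as recovered on day 21 and no modification follows.
- *If 'recovered' means recovery to the row's own 1000/100,000*, the first-occurrence rules apply. In Arm A, irinotecan goes from 50 × 5 = 250 to 40 × 5 = 200 mg/m² per cycle for recovery on days 22 to 28 (50/250 = 20% less). For days 29 to 34 it goes to 30 × 5 = 150 mg/m² (100/250 = 40% less). In Arm B, starting from 125 mg/m²/day, temozolomide goes from 125 × 5 = 625 to 100 × 5 = 500 mg/m² (125/625 = 20% less) in either window, with irinotecan also cut to 200 mg/m² for days 29 to 34.

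The tables do not say which reading is intended, so these reductions are possible consequences and not established ones. Steps 3 and 4 do not depend on the reading.

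**Unit slip in 9.2.** One litre is 1,000,000 mm³, so 100,000 per litre is 100,000 / 1,000,000 = 0.1 per mm³. The intended limit is evidently 100,000/mm³.

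**The case against.** **Section 9.2 does not order treatment.** Its sentence is a guiding principle that full doses are given only if counts recover. That is a necessary condition, and a site can satisfy both sections by waiting for the stricter 9.1 counts. This stands to a degree: a reader might infer that 9.2 requires full dose on time for the worked patient, and the wording does not go that far. But if no cycle may start below 1000/100,000, a marrow-specific full-dose threshold of 500/75,000 has little or no effect. The front-page amendment list (item d) records added instructions for bone marrow disease. An incomplete carry-over into 9.1 and the tables would fit that, though it is an inference.

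**The tables can be read through 9.2.** The 1000/100,000 in the 'recovered' rows describes the fall in counts, and the rows sit under the section that defines recovery. This is a fair reading. A reader might otherwise infer that the tables force a 20% or 40% reduction on every such patient, which the text does not settle. The argument does not reach 9.1, which prints its own numbers, or the Arm B day-34 row, which does not turn on the word 'recovered'.

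**The slips are trivial.** The unit may be a lost character from /µL, and no clinician would act on 0.1/mm³. That is agreed, but they fall in the sentence that has to be clarified anyway.

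**The lower limit is a clinical choice.** Keeping the stricter limit with a stated reason would also be coherent. That stands. The lower limit is proposed only because the sponsor already uses it in 7.4 and 9.2.

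**It may be too late.** Item (i) of the amendment list refers to VIT-versus-VI survival effects already seen, so dosing may have been largely complete at version 5.1. The document does not say. Section 10.2.3 allows up to 12 cycles and possible continuation, and 9.1 applies before each of them.

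**Conclusion.** The inconsistency is real and should be fixed. For patients with bone marrow disease, 9.1 in both arms and the day-34 row in Arm B apply limits of 1000 and 100,000/mm³ without the exception made in 7.4 and 9.2. A patient back at qualifying entry counts can therefore be delayed or discontinued although the full-dose threshold is met. Whether the 'recovered' rows also force a reduction is left open by the tables.

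The effect is confined to marrow-disease patients whose counts fall in the zone of disagreement. The protocol gives no number for them, so no frequency or loss of evaluable patients can be calculated. A reader might infer a threat to the sample size, the power or the comparison of the arms. The documents do not support that: the main analysis is by intention to treat, the 9.1 rule is common to both arms, and no stated design figure depends on these limits. This is a dosing-safety and consistency correction.

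**What to change.** 1. In 9.1, after the present limits, add: or, in case of bone marrow disease, ANC ≥ 500/mm³ and platelets ≥ 75 000/mm³. Leave the limits for all other patients as they are.
2. Add the same exception to the haematological rows of both the Arm A and Arm B tables in 9.2.1, including the Arm B day-34 row, so that both arms keep the same thresholds.
3. In the 9.2 sentence, replace 'or and' with 'and' for both pairs of limits, and print the general platelet limit as 100 000/mm³.
4. For patients already treated, list by arm those with bone marrow disease who were delayed, reduced or discontinued under the 1000/100,000 rule. If dosing has ended, this listing is the main remaining benefit: it shows whether any of those events followed from the rule and not from the drugs.

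The cost is one clause in 9.1, one added limit in the haematological rows of two tables, two corrections in 9.2, and one listing from dosing and blood-count data that the protocol already collects.
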